# 2.0 Hypothesis and Specific Aims

Aim 1: Determine which pain management method, L.M.X.4 Cream vs. J-tip 1% Xylocaine MPF Injection, provides the greatest pain relief to infants with clubfoot undergoing an inoffice percutaneous TAL. Hypothesis: J-tip 1% Xylocaine MPF injection will provide equal or greater pain control when compared to L.M.X.4 cream in infants undergoing an in-office percutaneous TAL.

Aim 2: Determine if there is a difference in the rate of adverse events between the two pain management methods, L.M.X.4 Cream vs. J-tip 1% Xylocaine MPF Injection. Hypothesis: J-tip 1% Xylocaine MPF injection will not be associated with an increased rate of adverse events in comparison to L.M.X.4 cream in infants undergoing an in-office percutaneous TAL.

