#### **Electronic Consent Process:**

In the event a potential study candidate is missed during a clinic visit, or research personnel are unavailable to consent in-person, study personnel will contact the patient's parent(s)/legal guardian(s) by phone to notify them of their child's study eligibility and ask if they would be interested in their child taking part. If the parent(s)/legal guardian(s) are interested in their child taking part in the study, study personnel will send a link to the REDCap-based electronic consent form by e-mail. If the parent(s)/legal guardian(s) agree for their child to take part in the study after reading the informed consent document, there will be an option for one parent/legal guardian to electronically sign their name and date the informed consent document. Once they electronically sign the electronic informed consent document, they will be given an option to save or print the signed electronic informed consent documents for their files.

We will seek to enroll 47 patients per group, 94 patients total in this study at each site.

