# Tenotomy

On the day of the subject's tenotomy they will receive pain control based on their group assignment- L.M.X.4 cream (with J-Tip Saline) or J-Tip with 0.25mL of 1% Xylocaine MPF (with placebo cream). The treating physician will provide a Dimeglio score. The following procedures will take place:

- Baseline: FLACC and pulse ox data will be recorded as baby is positioned on treatment table
- Application of randomized topical cream (either L.M.X.4 or placebo cream) for 30 minutes timed.
- Peak FLACC and pulse ox data will be recorded within 5 seconds of application of LMX 4 or Placebo Cream
- Consent for tenotomy procedure will be obtained (routine care).
- Baseline #2: FLACC and pulse ox data will be recorded 30 minutes after cream application
- Parents will leave room (routine care).
- Patient stays with healthcare staff (Physician, nurse, CCLS, cast tech, trained research assistant)
- Cream will be removed from the subject's foot (routine care). Peak FLACC and Pulse Ox will be recorded within 5 seconds after cream removal.
- Baseline #3: FLACC and pulse ox data will be recorded 30 seconds after cream removal
- J-Tip injection with 1% Xylocaine MPF or saline. Peak FLACC scale measurements and pulse ox measurements will be recorded within 5 seconds of injection (1st foot if bilateral)
- Following J-Tip injection there will be a 3-minute break, baby will be calmed during this time.
- Baseline #4: FLACC scale measurements and pulse ox measurements 3 minutes after J-Tip injection
- Tenotomy will be performed
  - FLACC Scale data and Pulse Ox data will be measured during the following events:
    - Percutaneous incision for TAL (1st foot if bilateral)- Peak FLACC scale and Pulse Ox data will be recorded within 5 seconds of poke of scalpel
    - Start of casting, after cast padding placed (1st cast if bilateral)

• End of casting (2nd cast if bilateral)

Adverse local effects of the cream and/or J-Tip injection will be noted (skin redness, swelling, rash, etc). Procedural complications will be recorded (excessive bleeding, concern for neurovascular injury, etc).

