# 10.0 Statistical Considerations

# **Power Analysis**

A power analysis was conducted to determine the sample size needed to find a clinically meaningful difference of 2.5 point in the FLACC score (SD=3) between the two methods. With alpha=0.05, power=0.8, and and effect size d=.83, at least 24 patients per group are required (N=48). Assuming a 20% participant lost to follow-up rate, we will need to enroll 29 patients per group (N=58).

An interim power analysis was conducted to determine the sample size to find a clinically meaningful difference of 2.0 points in the FLACC score between the two methods. This was performed using the maximum SD of the FLACC score observations of the first 39 patients (SD=4.13). With alpha=0.05 and power=0.8, at least 47 patients per group are required (N=94).

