# Data Analysis

FLACC, heart rate, and oxygen saturation will be measured at 10 distinct time points (Table 1) during serial casting and following in-office TAL. Changes in FLACC score, heart rate, and oxygen saturation will be compared between treatment and control cohorts utilizing a two-way ANOVA with a Geisser-Greenhouse correction for matched time measures. A Sidak's multiple comparisons test will be utilized to assess differences between cohorts at each of the 10 time points assessed. To compare number of

complications between cohorts, data will be collected at 3-weeks post TAL and analyzed using a non-parametric Mann-Whitney test, given the ordinal nature of the data. Similar non-parametric analysis with correction for multiple comparisons between cohorts will be utilized to assess changes in responses to REDCap surveys. Statistical analysis will be conducted utilizing GraphPad Prism 8.3.0. Statistical significance will be p<0.05.

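### The stated 80% power is for one unadjusted two-group FLACC comparison, but the analysis plan is an ANOVA with no deciding term plus ten Sidak-adjusted tests with no primary time point

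*Combined protocol and SAP*

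**What the plan says.** **Aim.** Section 2.0 (Aim 1) asks which method "provides the greatest pain relief to infants with clubfoot undergoing an inoffice percutaneous TAL". FLACC is clearly the intended measure, but the aim names no time point.

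**Power Analysis (section 10.0).** The first calculation uses a 2.5-point FLACC difference and SD 3, giving 24 per group. The current one uses a 2.0-point difference and the largest SD seen in the first 39 patients, 4.13. It concludes: "With alpha=0.05 and power=0.8, at least 47 patients per group are required (N=94" in total. Neither calculation mentions a time point, a change score, an ANOVA term or a multiplicity adjustment.

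**Data Analysis (section 10.0).** Changes in FLACC, heart rate and saturation over ten time points are compared between arms "utilizing a two-way ANOVA with a Geisser-Greenhouse correction for matched time measures". A Sidak "multiple comparisons test will be utilized to assess differences between cohorts at each of the 10 time points assessed" follows. The threshold is given once: "Statistical significance will be p<0.05". The text does not say which ANOVA term answers Aim 1, which time point is primary, or which baseline a change is measured from.

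**Tenotomy (section 6.0).** Ten readings are listed for the day, four of them labelled as baselines. One is the reading at incision: "Peak FLACC scale and Pulse Ox data will be recorded within 5 seconds of poke of scalpel". None is marked as primary.

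**Enrollment (section 5.0).** The target reads: "We will seek to enroll 47 patients per group, 94 patients total in this study at each site".

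**The concern.** A power statement is useful only if it describes the test that will be reported. Here the sample size rests on one unadjusted comparison, while the analysis offers a group term, an interaction and ten adjusted comparisons. For the same true effect these have very different power.

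Two things are at stake. First, a real difference at the incision could be missed: averaged over ten readings, some taken before any study product can act, it almost disappears from the group term, and at a single Sidak-adjusted time point it faces a much stricter threshold. Second, Sidak protects only its own ten comparisons. The plan does not say how a significant group term, interaction or single time point would be weighed against one another when Aim 1 is reported.

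**Working it through.** **Inputs from the documents.** Difference 2.5 with SD 3 (first calculation); difference 2.0 with SD 4.13, alpha 0.05, power 0.8 and 47 per group (current calculation); ten time points; 1:1 allocation. Sidedness is not stated, so two-sided is assumed. No dropout is applied.

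**1. What kind of test was sized.** For a two-sample t-test, the noncentrality is d × √(n/2) with 2n − 2 degrees of freedom.
- First calculation: d = 2.5/3 = 0.833 and n = 24 give noncentrality 2.887 against a critical value of 2.013, so power is 80.7%. The stated 24 therefore reproduces as one unadjusted two-sided comparison.
- Current calculation: d = 2.0/4.13 = 0.484 and n = 47 give noncentrality 2.348 against 1.986, so power is 64.2%. Reaching 80% needs 68 per group. This is a separate sample-size error and is not counted here.

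**2. The Sidak threshold.** Per-comparison alpha = 1 − 0.95^(1/10) = 0.0051.

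**3. What Sidak alone does to one time point.**

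| Situation | Unadjusted at 0.05 | After Sidak |
|---|---|---|
| Effect giving exactly 80%, 24 per group | 80% | 47.6% |
| Effect giving exactly 80%, 47 per group | 80% | 48.9% |
| Effect giving exactly 80%, 94 per group | 80% | 49.5% |
| 2.0 / 4.13, 47 per group | 64.2% | 30.8% |
| 2.0 / 4.13, 94 per group | 91.0% | 68.6% |

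The 94-per-group rows apply if the words on each site in section 5.0 mean 94 patients at each of two sites.

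**4. ANOVA terms at 47 per group (illustration).** Assumed, because the plan gives none of it: SD 4.13 at every time point, compound symmetry, within-patient correlation ρ of 0.2 to 0.5, normal data.
- Group term: a t-test on the patient mean, whose SD is 4.13 × √((1 + 9ρ)/10). At ρ = 0.5 this is 3.06. A 2-point effect at one of ten points averages 0.2.
- Interaction: noncentral F with λ = (n/2) × Σ(e − ē)² / (SD²(1 − ρ)), before the Geisser-Greenhouse correction. For an incision-only effect, Σ(e − ē)² = 3.6, so λ = 23.5 × 3.6 / (17.06 × 0.8) = 6.2 at ρ = 0.2.

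| Assumed effect profile | Group term | Interaction |
|---|---|---|
| Incision only | 6–7% | 35–55% |
| Incision and both casting readings | 16–26% | 76–94% |
| Constant at all ten points | 88–99% | 5% |

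Simulation with the estimated Geisser-Greenhouse correction lowers the interaction figures slightly, to 32–53% and 74–94%.

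**5. False positives with no true difference.** In 20,000 simulated trials per setting at 47 per group, at least one of group term, interaction or any Sidak time point was significant in 11.6% (ρ = 0.2) and 10.0% (ρ = 0.5). In a separate simulation of 12,000 trials, the two ANOVA terms alone gave 9.3% and 9.1%, and adding the ten Sidak tests gave 11.2% and 10.3%. Most of the excess over 5% comes from having two ANOVA terms. A single incision test stays at about 5%.

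**The case against.** The strongest reply is that the plan follows a familiar pattern: an overall ANOVA, then multiplicity-adjusted follow-up at each time point. On that reading the ANOVA decides, Sidak is descriptive follow-up, and 31% is not the power of the deciding test. The difference between the two methods that the trial was sized on also most resembles the group term, which exceeds 80% under a constant effect; the interaction can exceed 80% when the effect covers incision and casting.

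Much of this stands. A reader might infer that none of the planned tests has 80% power, or that the trial's power is 31%. The documents support neither: some ANOVA terms pass 80% under some assumed profiles, and 31% applies only if one Sidak comparison decides Aim 1. But the plan does not name the group term or the interaction, and derives no power for either. The constant effect that favours the group term is implausible if the ten points are the tenotomy-day readings, because the first precedes any study product and the second falls within 5 seconds of cream application.

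Two further cautions also stand. SD 4.13 is the maximum observed, so other time points have equal or smaller SDs and could have more power; the SD at incision and the SD of a change score are not given. And Table 1 is not in the text available, so it cannot be excluded that it marks a key time point. A list of time points would still not say which test decides.

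**Conclusion.** The point holds: the 80% is not tied to the planned analysis, because the plan does not say which test decides Aim 1. This should be fixed.

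The loss that belongs to this point is the Sidak adjustment: a true 80% becomes about 49%, or 64% becomes 31% with the current inputs at 47 per group. These figures assume a two-sided two-sample t-test, no dropout and, for the current inputs, SD 4.13. The step from 80% to 64% should not be charged to this point, because it comes from 47 per group being given where 68 are needed.

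The ANOVA figures, from about 6% to 99% for the group term, show how far power depends on the unstated profile and correlation; they are not estimates for this trial.

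A reader might also infer that the plan carries a 10–12% false-positive rate. That holds only if any of the three routes may count as success, a rule that the plan neither states nor excludes. It is a reason to name the deciding test, not a demonstrated property of the design.

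**What to change.** Without looking at results by arm, add to section 10.0:
- Peak FLACC within 5 seconds of the first-foot percutaneous incision is the single primary comparison for Aim 1, tested once between arms, two-sided at 0.05.
- The ANOVA and the Sidak comparisons, including those for heart rate and saturation, are secondary.
- The power of that one test is restated at the reconciled sample size. For a difference of 2.0 and SD 4.13 it is about 64% at 47 per group and 91% at 94 per group, noting that 4.13 is the maximum observed SD. Section 5.0 (47 per group at each site), section 10.0 (47 per group) and section 12.0 (24 per group) must first be made to agree.

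If another test is to decide, such as the group term, name it and state its power with the assumed effect profile and within-patient correlation.

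The cost is a short paragraph and no new data, since the incision reading is already collected. The downside is that an effect seen only at other time points could not decide Aim 1, and the restated power may fall below 80%.

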#### Clinical Visit around 21 days post-tenotomy (This visit is part of subject's routine care)

The subject will be assessed for complications. The treating physician will provide a Dimeglio score. A parental survey will be administered regarding quality of care, postoperative care, and perception of subject's pain level.

REDCap Survey questions to be sent to parents post TAL						
REDCap Survey	1. On a scale of 1-5, with 1 being no pain and 5 being extreme					
Postop Day 1	pain, how much pain is your child having today due to the					
	procedure?					
	2. On a scale of 1 to 5, with 1 being no irritability and 5 being					
	extreme irritability, how irritable is your child today due to the procedure?					
	3. How many doses of Tylenol (acetaminophen) has your child					
	been given today due to pain from the procedure?					
	4. If applicable, please list any other problems that your child is					
	having today, due to the procedure.					
REDCap Survey	1. On a scale of 1-5, with 1 being no pain and 5 being extreme					
Postop Day 7, 14	pain, how much pain has your child had over the last week due to					
& 21	the procedure?					
	2. On a scale of 1 to 5, with 1 being no irritability and 5 being					
	extreme irritability, how irritable has your child been over the last					
	week due to the procedure?					
	3. On average, how many doses of Tylenol (acetaminophen) per					
	day have been given to your child over the last week due to pain					
	experienced from procedure?					
	4. If applicable, please list any other problems your child has had					
	over the last week, due to the procedure.					

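### Aim 2 asks for a difference in adverse-event rates, but its only planned test is a p-value on an undefined number of complications, with no rate, risk difference or interval

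*Combined protocol and SAP*

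**What the plan says.** Section 2.0 sets Aim 2: "Determine if there is a difference in the rate of adverse events between the two pain management methods". Its hypothesis is that J-Tip "will not be associated with an increased rate of adverse events in comparison to L.M.X.4 cream". No margin is given.

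Section 10.0, Data Analysis, contains the only between-arm safety comparison. It concerns the number of complications, with data collected three weeks after the tenotomy and "analyzed using a non-parametric Mann-Whitney test, given the ordinal nature of the data". No proportion, rate, risk difference, ratio or confidence interval is planned for any adverse event.

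Section 6.0, Tenotomy, records two kinds of event in separate sentences. One covers the products: "Adverse local effects of the cream and/or J-Tip injection will be noted (skin redness, swelling, rash, etc". The other covers the operation: "Procedural complications will be recorded (excessive bleeding, concern for neurovascular injury, etc". The visit around day 21 says only "The subject will be assessed for complications". The schedule of events puts adverse events and complications in a single row.

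Section 8.0 defines an adverse event by its timing relative to the product, whether or not it is related. Normal sequelae of the procedure are recorded only if they need treatment or are clinically significant. Severity and relationship to treatment are graded for each event. Section 10 uses neither.

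**The concern.** The aim and the analysis differ in two ways.

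First, the aim is on the scale of a rate, and the analysis returns only a p-value on ranks. This matters more than usual because the hypothesis is one of no increase. A p-value above 0.05 is what a small trial tends to produce whether or not an increase exists. Without an interval, the reader cannot tell a reassuring result from an uninformative one.

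Second, the events to be counted are not defined. If complications means procedural complications only, the local effects of the cream and the injection, which are the direct subject of Aim 2, are never compared. If it means everything, product effects and procedural events carry equal weight in one total. In a blinded 1:1 trial this mainly dilutes a product difference, and dilution favours the hypothesis of no increase. The choice between these readings would be made after the data are seen.

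**Working it through.** **No figure to reproduce.** The documents give no event rate, margin, power or sample size for Aim 2. Every event rate and count below is an assumption. The size used is 47 per arm (Section 5.0 and the interim power analysis in Section 10.0), with alpha 0.05 taken as two-sided.

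**1. Is the test itself at fault?** Take hypothetical counts of 10/47 v 3/47 infants, each scored 0 or 1. Mann-Whitney (tie-corrected, no continuity correction) gives p = 0.037; the uncorrected chi-square gives p = 0.036. On 0/1 data the two are almost the same test. What Mann-Whitney leaves out is the estimate: 21.3% − 6.4% = 14.9 points, Newcombe 95% interval 0.7 to 29.2.

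**2. Does it follow the event rate when an infant can have several events?** Let 5 infants have 3 events each in one arm and 5 infants have 1 event each in the other. That is 15 v 5 events, yet Mann-Whitney gives p = 0.86. The test responds mainly to how many infants are affected, not to how many events occur.

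**3. What can a non-significant result hide?** Take 3/47 in each arm, so p = 1 and the difference is 0. The Wilson limits for 3/47 are

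(p + z²/2n ± z√[p(1−p)/n + z²/4n²]) / (1 + z²/n), with p = 0.0638, n = 47, z = 1.96, giving 0.0219 to 0.1716.

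The Newcombe upper limit for the difference is √[(0.1716 − 0.0638)² + (0.0638 − 0.0219)²] = √(0.01162 + 0.00176) = 0.116. Identical observed rates are still compatible with an increase of about 11.6 points. The planned output would not show this.

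**4. Precision at 47 per arm.** The approximate 95% half-width is 1.96√[2p(1−p)/47]:

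| Common rate p | Half-width (points) | Power to detect a doubling |
|---|---|---|
| 2% | 5.7 | 8% |
| 5% | 8.8 | 15% |
| 10% | 12.1 | 27% |
| 20% | 16.2 | 56% |

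Excluding a 10-point increase with 80% power at one-sided 0.025 needs n = (1.960 + 0.842)² × 2p(1−p)/0.10² per arm, which is 75, 142 or 252 at rates of 5%, 10% or 20%.

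**5. Cost of pooling under the broad reading.** Assume product effects in 5% v 25% and an independent background b in both arms. Each arm's pooled rate is 1 − (1 − p)(1 − b). Power is for the two-proportion z-test, by exact enumeration at 47 per arm:

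| b | Pooled rates | Power |
|---|---|---|
| 0 | 5.0% v 25.0% | 83% |
| 2% | 6.9% v 26.5% | 77% |
| 5% | 9.75% v 28.75% | 67% |
| 10% | 14.5% v 32.5% | 55% |
| 20% | 24.0% v 40.0% | 39% |
| 30% | 33.5% v 47.5% | 28% |

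Simulating the planned Mann-Whitney on summed counts gives much the same: about 82–83% with no background, then 55–56%, 41% and 32–33% at b = 10%, 20% and 30%. The loss comes from pooling, not from the choice of test.

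**The case against.** The strongest reply is that a rank test on a count is legitimate, and that on mostly 0/1 data it costs no power against a two-proportion test. That stands. A reader might infer from the Section 10 wording that the test is invalid or that it causes the power loss; step 1 shows neither is so.

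It can also be said that the larger background rates are pessimistic. Section 1.0 describes the in-office tenotomy as safe with few emergency visits, and Section 8.0 leaves out normal sequelae unless they need treatment or are clinically significant. That is fair, and it is why the 2% and 5% rows are shown. The 20-point product difference has no support in the documents either.

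A reader might further assume that procedural complications have nothing to do with the anaesthetic, so that pooling adds only noise. The documents do not show this. The infant lumbar puncture trial summarised in Section 3.0 reports a relative risk of success of 2.0 with J-Tip (95% CI 1.01 to 3.93), so the method of anaesthesia may affect how a procedure goes. Procedural complications should therefore still be shown by arm.

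Nor would an endpoint limited to local effects match the aim. Section 8.0 counts events whether or not related, and Section 7.0 names heart-rhythm problems as a risk of both products.

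Finally, rates could simply be tabulated at reporting. That would leave open which events count until the data are known.

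**Conclusion.** The concern holds as a mismatch between aim and analysis. Aim 2 asks for a difference in rates, and Section 10 plans no rate, difference or interval. It tests an undefined number of complications and calls a count ordinal. These points follow from the text and need no assumption.

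The size of the pooling effect does depend on assumptions. At 5% v 25% and 47 per arm, power falls from about 83% to between 77% and 28% as the background rises from 2% to 30%. These figures illustrate the broad reading only; they are not a forecast for this trial. The text does not establish that events will be pooled. The narrow reading is equally open and arguably worse, because the anaesthetics' own effects would then have no comparison at all.

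This concerns a stated specific aim, not the pain comparison, and should be corrected before the data are analysed.

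**What to change.** In Section 10.0:

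- Define the Aim 2 endpoint as the proportion of infants with at least one adverse event as defined in Section 8.0. State how the rule on normal sequelae applies, and that events noted on the day of tenotomy are included as well as those found at three weeks.
- Report the proportion in each arm and the risk difference with a 95% score interval (Newcombe or Miettinen-Nurminen).
- Report the same for events graded likely or definitely related to study treatment, including adverse local effects and any heart-rhythm events. The grading is already collected.
- Tabulate procedural complications separately by arm.
- Remove the ordinal justification for this endpoint. Rank tests can stay for the 1–5 survey items.
- Base any statement of no increase on the upper limit of the interval, not on p > 0.05.

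The cost is minor analysis work and revised wording. Because the schedule combines adverse events and complications in one row, the sponsor should confirm that the case report form lets the two be told apart. The intervals will be wide at 47 per arm, as step 4 shows. That limit on what the trial can say about safety exists already; the change makes it visible.
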